During the consent process, study participants will be able to choose between being randomized between the low versus high dose strategy or the low dose versus moderate dose strategy. Moderate and high dose treatment participants will be combined for analysis as described below. The moderate and high treatment doses were chosen with help from our clinical advisory committee because they are generally considered safe and potentially effective among persons who meet our inclusion criteria based on medical history and baseline laboratory values (normal calcium and PTH, and negative COVID-19 antibodies). The low dose was selected to ensure that all subjects had a high likelihood of a total vitamin D intake that met the recommended daily allowance (RDA). All patients will be informed of whether their baseline calcium and PTH are normal. Patients who are still eligible for study participation after initial testing will be asked prior to randomization whether they are still willing to participate to maximize retention and minimize dropout. After randomization, subjects will be instructed to pick up their 9-month supply of vitamin D at either UCMC or Rush University corresponding to their randomized, blinded dose. For those unable to pick up their bottles in-person, the UCM IDS pharmacy will mail the subject their bottle. We propose a 3 to 9-month study period, depending on when the subject was recruited, as described in the study timeline of Section IV. Subjects recruited after September 30th will participate in the intervention 6 months to align with study timeline and funding. Subjects enrolled between January 1, 2023 and March 31, 2023 will take the study drug until June 2023, so at least 3 and no more than 6 months. Chart review for subjects will occur for 12 months after the active intervention period has ended. This study timeline is further detailed in Tables 1-4 of Section IV in the currently approved protocol document. Adverse events, defined as hypercalcemia or unexplained increased falls in either study arm will prompt discontinuation of the study medication and further evaluation as reported in the monitoring section below.

[figure not shown]
On the advice of our Clinical Advisory Council faculty members, patients who test for PTH >85pg/dL but have calcium levels <10mg/dL and low vitamin D (<30ng/mL) will be eligible to continue in the study because those

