The sample size was chosen to have at least 80% power to detect a 25% or larger decrease in the hazard of developing COVID-19 between study arms at  $p<0.05$  assuming a 30% baseline COVID-19 incidence rate over the study period, in line with the 3% per month incidence cited above.

*Individuals are eligible to enroll in the study if they:*

1. Are 18 years or older.
2. Live or work in the Chicagoland area (Illinois counties: Cook, Lake, McHenry, DuPage, Kane, Kendall, Grundy, Will, and Kankakee; Indiana counties: Lake and Porter).
3. Are interested in vitamin D as a potential preventive measure against COVID-19 in which they self-administer a daily dose of vitamin D during the 9-month study period.
4. Are willing to attend the laboratory for drop-in appointments at UChicago Medicine, Ingalls Hospital, or Rush University Medical Center every 3 months at up to 4 time points over up to a 9-month period for blood draws measuring COVID-19 antibodies, calcium, vitamin D and PTH levels.
5. Are willing to complete self-report measures at up to 4 time points over the course of up to 9 months by completing a 15-minute survey at intake by telephone or via web and 10-minute web-based follow-up surveys.

*Individuals are excluded from the study if they:*

1. Report being pregnant, planning to become pregnant, and/or report breastfeeding during the study period.
2. Report a history of chronic kidney disease, including a history of abnormal GFR and/or creatinine.
3. Report a history of hyperparathyroidism.
4. Report a history of increased falls.
5. Report a history of hypercalcemia.
6. Report a history of gastrointestinal absorptive disorders, including having undergone bariatric surgery.
7. Report a history of kidney stones (1 in past year or 2 in lifetime).

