For our primary outcome of COVID-19 infection as measured by patient report of clinically confirmed COVID-19 (or viral PCR when available) and secondary outcomes of COVID-19 antibody seroconversion and disease severity (hospitalization, ICU stay, ventilator use, death), hazard models will be employed to assess the effect of each vitamin D dosing strategy on the outcome. We will first develop hazard ratios for between-group analyses on the primary outcome using log-rank tests, and then develop Cox proportional hazard models to model the hazard function on a set of covariates including but not limited to, moderate or high vitamin D dose, baseline vitamin D levels, age, gender, race, ethnicity, sun exposure, sleep habits, exposure of cohabitants, job type, and study site. We will also control for randomization date to adjust the underlying hazard function for COVID-19 prevalence over time. While our primary analysis will pool subjects randomized to either the moderate or high dose and compare them to low dose subjects, we will also perform secondary analyses comparing low to moderate and low to high and additional analyses that use post randomization vitamin D levels as time varying covariates. The design thus seeks to maximize potential to find statistically significant results between different dosages given uncertainty in subject willingness to be randomized to different doses. As noted above, the sample size was chosen to have at least 80% power to detect a 25% or larger decrease in the hazard of developing COVID-19 between study arms at  $p<0.05$  assuming a 30% baseline 10-month COVID incidence over the study period, in line with the 3% monthly incidence cited above. As finding that a higher dose has no effect or a paradoxical adverse effect on COVID incidence would both lead to use of a lower dose given even the small risks of higher dose vitamin D, Ruxson and Neuhauser would argue for use of a 1-sided test, resulting in 80% power to detect a 20% or larger decrease.

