### Summary of Consent Form Versions

**For those consented March 31 2022-December 31, 2022:** We will use consent form Version 10 (UCMC) or Version 11 (Ingalls), both in English and Spanish. This is because these consent forms are written for those who participate in the study for 6-9 months. Subjects who consent before October 1, 2022 will be in the study for 9 months. Subjects who consent on or after October 1, 2022 will be in the study for 6 months. This information is also clarified in these consent forms and in Table 3 of Section IV above. Version 10, like Version 8, has language for opt-in labs while Version 11 does not. We will use consent form Version 4 for Rush subjects.

For those who consented using UCM Consent Version 8 or 9, or Rush Consent Version 3 (thus who consented on or after January 1, 2022 and in follow up for less than 6 months), we wish to allow for the option to re-consent these subjects on UCM Consent Version 10 or 11, or Rush Consent Version 4, to allow these subjects to participate in the study for a full 9-month period (and would thus receive 4 total blood tests and 4 follow-up

surveys). This re-consent is entirely voluntary. If these subjects do not wish to re-consent, they will end their time in the study June 30, 2022.

**For those consented January 2023-March 31, 2023:** We will use consent form Version 12 (UCMC) or Version 13 (Ingalls), both in English and Spanish. With the removal of the final PTH lab approved in Amendment 54, we will then use consent form Version 14 (UCMA) or Version 15 (Ingalls), both in English and Spanish. This is because these consent forms are written for those who participate in the study for less than 6 months. This information is also clarified in these consent forms and in Table 4 of Section IV above. Version 12 and 14, like Versions 8 and 10, have language for opt-in labs while Version 13 and 15 do not.

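### Power assumes ten months of risk, but no participant is on study drug for more than nine, and Section IX does not say when primary at-risk time ends

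*Combined protocol and SAP*

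**What the plan says.** **Power.** Section VIII gives at least 80% power for a 25% or larger hazard reduction at p<0.05, "assuming a 30% baseline COVID-19 incidence rate over the study period, in line with the 3% per month incidence cited above". Section IX repeats this and makes the period explicit: "assuming a 30% baseline 10-month COVID incidence over the study period, in line with the 3% monthly incidence cited above". It adds that methodologists it names "would argue for use of a 1-sided test, resulting in 80% power to detect a 20% or larger decrease".

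**Length of intervention.** The Section III Summary states: "We propose a 3 to 9-month study period, depending on when the subject was recruited". Recruits from October 2022 have 6 months; the consent-version summary in Section XIV says "Subjects who consent on or after October 1, 2022 will be in the study for 6 months". Those enrolled from January to March 2023 "will take the study drug until June 2023, so at least 3 and no more than 6 months". Recruits of early 2022 were due to stop at the end of June 2022, but may re-consent "to allow these subjects to participate in the study for a full 9-month period". On the short cohorts, Section IV says only that the analyses will be adjusted accordingly. It gives no event count, power figure, cohort share or dropout rate.

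**At-risk time.** Section IX defines the primary outcome as a patient report of confirmed COVID-19, or PCR where there is one. It specifies log-rank tests and Cox models, with no censoring date. Three other sections bear on the window:

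- Section III (Procedures and Materials): surveys at months 3, 6 and 9 ask for a confirmed diagnosis and its date, and positive PCR results are self-reported in the quarterly survey.
- Section IV, Tables 1-4: chart review for positive tests runs for 12 months after participation. The Note below Table 4 says that overdue final surveys will be pursued past the study end date.
- Section III (Procedures and Materials): participants learn their dose when the intervention has ended for everyone in the protocol. Those who move to protocol 20-0847 learn it later.

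**The concern.** In a time-to-event comparison, power depends on the number of events, and so on how long participants are at risk. The plan takes its event count from a period longer than any participant spends on drug, and the count was not revised when shorter cohorts were added. If the shorter periods govern the primary analysis, both power figures are too high.

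The missing end of at-risk time matters more. If the chart-review year counts, events that occur off drug, and for the last cohorts after unblinding, enter the primary comparison. Both the hazard ratio and the power then depend on how much effect persists after stopping, on which the documents are silent. Without a stated rule, the window could be chosen after the data are seen.

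**Working it through.** **Inputs.** 2,000 randomized 1:1, so 1,000 per arm (Section III). HR 0.75, two-sided 0.05. HR 0.80, one-sided 0.05. Control incidence 30% at 10 months, or 3% per month (Sections VIII and IX). Section VIII does not state sidedness; two-sided is inferred because Section IX offers one-sided as the alternative. No dropout is stated, so none is applied.

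**Formulas.** Control incidence p0 by month T has three readings: summed, 0.03T; constant hazard through 30% at 10 months, 1 - 0.7^(T/10); compounded, 1 - 0.97^T. Expected events d = 1000 × [p0 + 1 - (1 - p0)^HR]. Schoenfeld power = Φ(√(d/4) × |ln HR| - z), with z = 1.960 or 1.645.

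**The plan's own figures (p0 = 0.30).**

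- HR 0.75: d = 1000 × (0.300 + 1 - 0.7^0.75) = 535; √(535/4) × 0.2877 - 1.960 = 1.366; power 91.4%.
- HR 0.80: d = 548; √(548/4) × 0.2231 - 1.645 = 0.967; power 83.3%.

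Both statements hold on the stated input.

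**At-risk time ending with the intervention.** At T = 9 and HR 0.75, the three readings give 480, 489 and 426 events; at HR 0.80 they give 493, 501 and 437. For 80% power, about 379 events are needed at HR 0.75 and 497 at HR 0.80. The cohort mixes below are assumptions, because the documents give no shares. Each cell shows summed / constant hazard / compounded.

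| Follow-up | Two-sided, HR 0.75 (%) | One-sided, HR 0.80 (%) |
|---|---|---|
| All at 9 months | 88.3 / 88.9 / 84.3 | 79.7 / 80.3 / 75.4 |
| 10% at 6 months, rest 9 | 87.3 / 87.9 / 83.2 | 78.5 / 79.2 / 74.2 |
| 25% at 6 months, rest 9 | 85.5 / 86.4 / 81.4 | 76.6 / 77.5 / 72.4 |
| 50% at 6 months, rest 9 | 82.0 / 83.4 / 78.0 | 73.0 / 74.4 / 69.2 |
| All at 6 months (bound only) | 72.8 / 75.7 / 69.5 | 64.5 / 67.1 / 61.7 |

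**Break-even share at 6 months** = (d9 - d_required) / (d9 - d6), on unrounded event counts. Two-sided: 62% / 74% / 35%. One-sided: 3% on the constant-hazard reading; on the other two, power is already below 80% with everyone at 9 months.

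**Dropout.** An assumed 10% loss, at the stated 30% incidence and with no other change, gives 88.4% two-sided and 79.8% one-sided.

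**Chart-review year counted, 9-month cohort.** The log hazard ratio is averaged over on-drug and off-drug events, and power uses all events. With HR 0.75 on drug and no effect afterwards:

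- Compounded: 426 + 482 = 908 events; mean |ln HR| = 426 × 0.2877 / 908 = 0.135, an apparent HR of 0.874; power 52.9%.
- Constant hazard: 489 + 526 = 1,015 events; apparent HR 0.871; power 59.7%.

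With full persistence, two-sided power is about 99%. The one-sided test at HR 0.80 gives 48.6-54.1% with no off-drug effect, 78.5-83.0% with an off-drug HR of 0.90, and 95.1-96.7% with full persistence.

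**The case against.** The strongest reply has four parts.

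1. **The basis for the sample size survives.** The number of participants was chosen for at least 80% power at a 25% reduction. That reproduces at 91%, and with everyone at 9 months it holds on all three readings. A reader might infer that the trial is underpowered for its design basis. The documents do not support that: they give no cohort shares, and on the plan's own incidence scale more than about three in five participants would have to be limited to 6 months.
2. **The one-sided sentence is an aside.** It reports what others would argue and does not set the sample size. With everyone at 9 months it rounds to the stated 80%, and with an assumed 10% at 6 months the shortfall is under 2 points. The plan also equates 3% per month with 30% over 10 months, which is summing, so the compounded column is a sensitivity case. These points stand and limit the size of the finding.
3. **The shortfall is conditional.** A reader might infer that the one-sided claim simply fails. It falls short only if risk time ends with the drug; if the chart-review year counts and the effect persists, power exceeds 80%. That is right, and it is why the window has to be stated.
4. **The surveys already suggest the window.** Both parts of the primary outcome have a survey source during the intervention, and dated diagnoses make late surveys manageable. This narrows the ambiguity. It does not remove it, because Section IV also collects positive tests by chart review for 12 months to measure outcomes, and Section IX does not exclude them. A reader might infer that off-drug events will be counted; the documents do not say so either.

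The non-proportional-hazards fallback and the adjustment for randomization date in Section IX change the model, not the window.

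**Conclusion.** The point holds in conditional form and should be fixed. The stated power rests on a follow-up length that the design does not have. This is an outdated planning input, not an arithmetic error, since the stated 30% reproduces both claims.

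If at-risk time ends with the intervention, the two-sided figure loses 2 to 7 points at 9 months but keeps its 80% floor in most mixes. The one-sided figure has no reserve at 9 months, and any material share of shorter follow-up takes it below 80%.

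The unstated end of at-risk time has the larger effect. For a 9-month cohort, counting the chart-review year moves two-sided power from 84-89% to as low as 53% or as high as 99%, depending on carry-over. These figures assume 1,000 per arm, proportional hazards while on drug, no dropout except where shown, and cohort mixes that the documents do not give.

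**What to change.** 1. In Sections VIII and IX, replace the 30% ten-month input with control incidence over the actual 9-, 6- and 3-month periods, weighted by the cohort mix after re-consents and with a stated dropout. State how 3% per month accumulates. Restate the two-sided power, and restate or delete the one-sided figure.
2. In Section IX, define primary at-risk time as randomization to the end of the participant's assigned intervention period, and censor there. Use the diagnosis date already collected in the surveys, including late ones. Report later chart-review positives as a secondary analysis. Another window could be defended, but this one keeps off-drug and partly unblinded events out of the primary comparison.

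The cost is a short recalculation and a few sentences, with no extra participants or procedures. The stated power becomes less favourable, and later events leave the primary analysis.

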
administered to subjects post-randomization over the phone or via web-based survey at baseline, depending on subject preference, and every 3 months thereafter via a web-based instrument. Subjects will be given the option to call the study team and complete the survey over the phone in reminder emails. Survey and laboratory records will be maintained and monitored by study staff on encrypted, password-protected devices in compliance with UCM and RU IRB Information Security Office standards. Electronic Medical Records will be reviewed for predictors and indicators of COVID-19 and for severity of infection if subject has had a positive COVID-19 test result.

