8. Report already taking more than 400 IU of vitamin D daily as recommended by their health care provider, excluding multivitamins and excluding supplements that include vitamin D and calcium together, unless permission is received from the prescribing health care provider to participate. In this case, no more than 1,000 IU vitamin D may be taken daily in addition to the study medication and we would limit the subjects to participation in the low vs. moderate arm of the study, producing a maximum dose of 5,000 IU per day. We note that the NAM recommended a maximum dose of 4,000 IU per day without medical supervision based on evidence that 5,000 was safe and known uncertainty about the precision of dosing in 5,000 IU supplements available over the counter. However, since we are testing the dosage of our 4,000 IU supplements to high precision and these patients would be taking their original supplements with a labelled dose of 1,000 IU or less, we think that the combination of our 4,000 IU supplements and the patient's original supplement of up to 1,000 IU should not provide a maximum dose meaningfully above the 5,000 IU actual dose the NAM has considered safe for taking without medical supervision. We note further that we are measuring vitamin D levels and PTH in these patients regardless in this study. We do, however, have another study of vitamin D and COVID (IRB# 20-0847), in which we are not measuring these levels, for which it is more important to not substantially exceed NAM maximum level of 5,000 IU per day. The approach described here allows us to align the approach in these two studies.
9. Report taking D2.
10. Report a history of sarcoidosis.

11. Screen positive for hypercalcemia ( at UCM, defined as >10.4 mg/dL and at Rush, defined as >11.2 mg/dL) during the initial blood test.
12. Screen positive for hyperparathyroidism (PTH>85 pg/dL) during the initial blood test with calcium  $\geq 10$ mg/dL and normal levels of vitamin D ( $\geq 30$ ng/mL)
13. Have vitamin D levels of >100ng/mL at study start, or >250ng/mL during follow-up labs.
14. Are unwilling to provide blood samples during quarterly blood tests.
15. Are unwilling to take daily vitamin D.

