The proportional hazards assumption will be assessed using the *estat phtest* command in Stata with rejection of proportion hazards defined by  $p<0.05$  for any variable or the global test, or by visual assessment of Schoenfeld residuals. Continuous variables which fail proportional hazards will be categorized. For any categorical variable or categorized continuous variable which fail proportional hazards, we will perform Cox regression which stratifies based on that variable. If moderate or high dose vitamin D variables fail the proportional hazards assumption, we will estimate non-proportional hazards models. Assuming missingness at random, we will impute missing values of covariates with multiple imputation by chained equations with 20 imputations. Covariates in the imputation will include the covariates in the primary analysis excluding moderate or high dose vitamin D variables. Data analysis will be executed in Stata 18.0.

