### Protections Against Potential Risks

The risks as described in "Potential Risks" we believe to be unlikely and will be mitigated whenever possible. The nature of the intervention and all risks will be fully described to subjects, moreover, subjects will be informed that they can choose to discontinue and withdraw from the study at any time. Subjects can also choose to not answer any question on the survey. For the risk of loss to confidentiality, all members of the study team will maintain strict standards for confidentiality, further described in Section XIV and thus not repeated here. The risk of complications due to venipuncture will be mitigated by use of trained professional phlebotomists at UCM and RU. The risks of complications due to higher doses of vitamin D will be mitigated with the exclusion criteria as outlined above during preliminary screening and through subject education of symptoms for fall risk. Vitamin D-mediated hypercalcemia will be mitigated by regular monitoring by investigators for critical calcium values during blood draws and subject education of symptoms related to hypercalcemia. Subjects at UCM will be referred to their primary care provider if they experience these symptoms or have calcium levels of 10.5-12 mg/dL and subjects at Rush will be referred to their primary care provider if they experience these symptoms or have calcium levels of 11.3-12mg/dL. For all subjects, if calcium laboratory values are 12.1mg/dL-14mg/dL, subjects will be advised to go to urgent care and if values are greater than 14 mg/dL subjects will be advised to seek care at an emergency room. Subjects will be provided with the pager number of an on-call physician at UCM and Rush primary care group that they can use in the event of emergent symptoms.

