At the beginning of the consent process, subjects will be asked to verify their identity by emailing or texting the study email or study cell phone a photo of their diver's license, state ID, passport or employee ID. They will be asked for their email address where a signed copy of the consent form will be sent for their records. In the consent form, subjects will be informed about the nature of the intervention, that they will be receiving a daily dose of vitamin D, either low or moderate/high, and must self-administer this dose each day. They will be informed about the nature of the intervention, that they are blinded to the dose they receive. Subjects will be reminded that participation is entirely voluntary, and they may withdraw at any time without consequence. Subjects will also be informed about the data collection methods, including the survey and testing they will undergo at each stage, and that they will be informed about test results for COVID-19 antibodies only during the study period. They will be informed that their PTH, calcium and vitamin D results will be withheld until completion of study participation unless they suggest a safety concern. They will be educated about the risks of the study as described above in "Potential Risks". Subjects will be informed about what will be done if they are found to be hypercalcemic: First, they will be told to cease vitamin D supplementation. Subjects at UCM with a calcium level 10.5-12 mg/dL and at Rush with a calcium level 11.3-12mg/dL will be instructed to consult with their primary care physician. All subjects with a calcium level of 12.1-14 mg/dL will be referred to urgent care. All subjects with a calcium level greater than 14 mg/dL will be referred to the emergency room. These participants will continue to undergo monitoring blood draws and surveys and may resume vitamin D supplementation per study protocol with a physician note.

Subjects will then be instructed to select their randomization preference on the consent form. If a potential subject says they are already taking a supplement or supplements that contains 2,000IU or less of vitamin D in total, they may continue to take those supplements while part of the study, however, they will only be allowed to enroll in the arm that randomized them between 400 and 4,000IU.

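### The imputation rule lists the analysis covariates, excludes dose and does not provide for the outcome: this weakens covariate adjustment and, only under three further conditions, separates the two secondary dose contrasts (minor)

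*Combined protocol and SAP*

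**What the plan says.** Section IX imputes missing covariates by chained equations under a missing-at-random assumption, with 20 imputed data sets. The only statement of what enters the imputation is "Covariates in the imputation will include the covariates in the primary analysis excluding moderate or high dose vitamin D variables". Nothing elsewhere adds the event indicator, follow-up time or cumulative hazard.

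The Cox covariate list in the same section is open-ended. It names baseline vitamin D, demographic items and "sun exposure, sleep habits, exposure of cohabitants, job type, and study site". The primary contrast pools moderate and high dose against low dose. In addition, "we will also perform secondary analyses comparing low to moderate and low to high". The plan does not say which low-dose subjects serve as comparator in those two analyses, and the list neither names nor rules out a term for the randomisation option.

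The option is not randomised. The Section III Summary says "study participants will be able to choose between being randomized between the low versus high dose strategy" or the low-versus-moderate one. Some existing supplement users are confined to the latter: "we would limit the subjects to participation in the low vs. moderate arm of the study" (Section VIII) and "they will only be allowed to enroll in the arm that randomized them between 400 and 4,000IU" (Section XIV).

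Sun exposure, sleep, cohabitant exposure and job type come from the intake survey. Section III, Procedures and Materials, describes it as "administered to subjects post-randomization over the phone or via web-based survey at baseline", whereas Appendix A, step 5, sends it directly after consent. Section X adds: "Subjects can also choose to not answer any question on the survey".

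**The concern.** If imputed values are drawn without the outcome, they carry no association with COVID-19 beyond what the other covariates supply. The covariate's coefficient is diluted and adjustment for it is incomplete.

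For a randomised comparison this matters little. Dose, however, is randomised only within an option. If the moderate group is compared with all low-dose subjects, half of whom may have chosen the other option, the contrast leans on covariate adjustment. Dropping dose from the imputation weakens it further, because imputed values ignore any covariate difference between dose groups. The residual confounding could then look like a difference between 4,000 and 10,000 IU.

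**Working it through.** The plan gives no figure for missingness or for the effect of imputation, so there is none to reproduce.

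**Inputs.** From the documents: N = 2,000, 1:1 low versus higher dose, HR 0.75, 30% baseline risk. Assumed: missing fraction *m*, covariate log HR β, and the difference δ in covariate mean (in SD) between those choosing the high and the moderate option. Options are assumed to split 50/50, with missingness completely at random unless stated.

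**Approximation.**

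1. Covariate coefficient under the listed rule: β* ≈ (1 − m)β.
2. With all low-dose subjects as comparator, the moderate group lies δ/2 below them on the covariate and the high group δ/2 above. In the imputed data this gap is about (1 − m)δ/2.
3. Adjustment removes (1 − m)²βδ/2, so βδ/2 × [1 − (1 − m)²] remains as bias.
4. Adding the outcome only restores β but not the gap, leaving m × βδ/2.
5. For the pooled contrast, and for same-option contrasts, randomisation makes the expected gap zero.

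**Setting A.** Covariate HR 1.5 per SD, δ = 0.5, so βδ/2 = 0.405 × 0.25 = 0.101. Simulation: 250 trials, 10 imputations, one fully observed covariate correlated 0.3. Complete data gave moderate/high 0.753/0.752, pooled 0.753 and covariate HR 1.504.

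| m | Formula bias | Moderate/high HR, listed rule | Moderate log shift | Covariate HR | Pooled HR |
|---|---|---|---|---|---|
| 10% | 0.101 × 0.19 = 0.019 | 0.738/0.767 | ln(0.738/0.753) = −0.020 | 1.440 | 0.755 |
| 20% | 0.101 × 0.36 = 0.036 | 0.725/0.781 | ln(0.725/0.753) = −0.038 | 1.380 | 0.755 |
| 40% | 0.101 × 0.64 = 0.065 | 0.706/0.803 | ln(0.706/0.753) = −0.064 | 1.271 | 0.757 |

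At 20% missing the attenuation is 1 − ln(1.380)/ln(1.504) = 1 − 0.322/0.408 = 21%. Adding the outcome only gives 0.738/0.768 (shift −0.020; formula 0.2 × 0.101 = 0.020). Adding outcome, dose and option gives 0.753/0.752.

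**Setting B.** Covariate log HR 0.50, odds ratio 1.65 per SD for choosing high, 20% missing (200 trials, 10 imputations).

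- Complete data: 0.739/0.747, pooled 0.746, covariate log HR 0.504.
- Listed rule: 0.711/0.776, pooled 0.748, covariate 0.399 (1 − 0.399/0.504 = 21% attenuation).
- With outcome, dose and option: 0.740/0.749, pooled 0.747, covariate 0.502.

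The log shifts are ln(0.711/0.739) = −0.039 and ln(0.776/0.747) = +0.038. Against a standard error of 0.13 to 0.14, that is about 0.3 of a standard error. A separate run of this setting gave 0.704/0.790 against 0.735/0.761 complete.

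**Do the conditions matter?** Each check keeps the listed imputation rule.

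- *Same-option comparator* (Setting A, 20%): 0.756/0.753 against 0.754/0.752 complete. No separation.
- *Option added to the Cox model* (separate run of Setting B): 0.737/0.762 against 0.735/0.761 complete. No separation.
- *No covariate difference between options* (40% missing, covariate HR 2): 0.763/0.764. No separation.

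**Sensitivity.**

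- If missingness depends on another covariate or on the event, attenuation at 20% missing is 27 to 32%.
- In a deliberately strong case (HR 2 per SD, δ = 1, 20% missing) the contrasts become 0.647/0.846 against 0.751/0.754. At 40% missing, the pooled HR there moves only from 0.754 to 0.767.
- If subjects lacking the intake survey are followed for only 0 or 3 months, attenuation falls to about 5 to 6%, and the Setting B contrasts are 0.728/0.738 against 0.734/0.732.

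**The case against.** **The wording may be innocent.** A list of imputation covariates need not mention the outcome, and adding it is not forbidden. The dose exclusion may only mean that dose is complete and needs no imputing. That is possible, but an analyst following the sentence as written would build the model examined here. The point is conditional on that reading.

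**The imputation rule is not the root of the secondary problem.** This largely stands. A same-option comparator or an option term removes the separation with the imputation rule unchanged. Conversely, better imputation cannot remove unmeasured differences between option groups. The fix therefore needs both parts.

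**Missingness may be small.** Telephone completion and reminders reduce non-response, baseline vitamin D is drawn before randomisation, and the documents disagree on when the intake survey is sent. Non-completers may also have little outcome follow-up, since the primary outcome is itself survey-reported. All of this lowers the likely size.

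**The link to option is assumed.** Beyond subject choice, the only documented determinant is supplement use. Nothing ties sun exposure, sleep, cohabitants or job type to the option. This too stands. Covariate HRs are also not a study aim.

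**Stronger readings.** A reader might infer that leaving out dose and outcome biases the primary result. The documents do not support that: the log-rank test uses no imputed data, and the pooled contrast is balanced by randomisation within option. A reader might also infer that the plan will produce a false difference between 4,000 and 10,000 IU. It would do so only if all three conditions hold, and the plan fixes none of them.

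**Conclusion.** The concern holds in a limited form and is minor. Read as the full list, the rule attenuates the log HR of an incomplete prognostic covariate by roughly its missing fraction under completely random missingness: more if missingness depends on the event or another covariate, less if non-completers have short follow-up. The primary conclusion is not at risk.

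The secondary contrasts separate only with an all-low comparator, no option term, and an incomplete prognostic covariate that differs between option groups. Even then, at the assumed 20% missing and moderate associations, the shift is well below the standard error. It is nevertheless systematic, and more imputations would not reduce it. Its direction reverses if the covariate is linked to choice the other way. Missing fraction, covariate effect and link to option are all assumptions.

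**What to change.** In Section IX, replace the imputation sentence with:

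> *The imputation model will include all analysis covariates, randomised dose, the chosen randomisation option, and the event indicator and Nelson-Aalen cumulative hazard of the outcome analysed.*

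For low vs moderate and low vs high, also include or stratify by the chosen option in the Cox model, or restrict the comparator to low-dose subjects with the same option. Keep the 20 imputations.

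Option must accompany dose in the imputation. With outcome and dose but no option, the same-option contrasts at 20% missing in Setting A become 0.769/0.737, against 0.754/0.751 with option.

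The cost is two text changes using variables already collected, plus an imputation run per outcome. For severity outcomes with very few events (ICU stay, ventilator use, death), use the primary-outcome imputations or a simpler model to avoid separation in the imputation regressions. The log-rank test is unchanged. The statements on intake-survey timing in Section III and Appendix A should also be reconciled, because the timing bears on how much is missing.
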